#### Sample Size Determination

Based on previously acquired prospective outcomes data (unpublished), we will conservatively estimate a positive response rate of 50% in our experimental arm (see *Preliminary Studies*). In a meta-analysis examining sham procedures, our group found a maximum placebo response of 30% ([name], unpublished). Therefore, to obtain a power of 0.8 (alpha 0.05) to detect superiority of the blood and fibrin glue patching group, assuming positive response rates of 50% for the patching group and 30% for the control group, we would need a total of 148 patients (74 patients in each arm).

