**Timeline of Events**

**Patient Outcome Measures and Crossover**

**Headache Impact Test (HIT-6):** A validated headache assessment tool with good internal consistency and test-retest reliability that is designed to provide a global measure of headache impact in six domains [32]. Scores range from 36 (asymptomatic) to 78 (severe headache). Score ranges: 36-49 (little or no headache impact), 50-55 (some impact), 56-59 (substantial impact), and >60 (severe impact) [33, 34]. Prior studies have determined that the minimally important clinical difference between groups is 1.5 points for the HIT-6 [35].

**EQ-5D:** A standardized measure of health status that provides a simple, generic measure of health for clinical appraisal [36]. It is well-validated for health status measurement [37] and for quality-of-life in headache [34].

**Patient Global Impression of Change (PGIC):** A validated 7-point Likert-type scale assessing a patient’s overall impression of improvement after intervention [38, 39].

**Work Productivity and Activity Impairment (WPAI):** A validated instrument with good test-retest reliability used extensively in health research [40, 41] that quantifies impairment in daily activities and work productivity [42].

**Crossover:** Patients will be permitted to crossover to the other treatment arm two months after the procedure.

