**Statistics**

**Patient Outcome Analysis**

The change in HIT-6 from a pre-procedural score of > 56 (substantial or severe impact on life) will be considered for each group at each time point. *Primary Endpoint (HIT-6 at 1 month)*: We will apply a two-sample t test, or in the cases of low counts and non-parametric data a Wilcoxon Rank Sum test, to test the primary endpoint. *Secondary Endpoints*: The same analysis will be employed for all secondary endpoints at each time point.

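### The stated 80% power belongs to a comparison of response rates that the plan does not run; the power of the planned HIT-6 test is not given

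*Combined protocol and SAP*

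**What the plan says.** **Sample size.** Sample Size Determination derives 148 patients (74 per arm) from a comparison of response rates, "assuming positive response rates of 50% for the patching group and 30% for the control group". The 50% is attributed to unpublished prospective outcomes data and the 30% to an unpublished meta-analysis of sham procedures. The stated aim of the calculation is "to obtain a power of 0.8 (alpha 0.05) to detect superiority of the blood and fibrin glue patching group". The paragraph does not say whether alpha is one- or two-sided.

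**Primary analysis.** Patient Outcome Analysis names HIT-6 at 1 month as the primary endpoint and speaks of change from a baseline score above 56. The test is specified as follows: "We will apply a two-sample t test, or in the cases of low counts and non-parametric data a Wilcoxon Rank Sum test". For the rest, "The same analysis will be employed for all secondary endpoints at each time point".

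**Benchmark.** Patient Outcome Measures and Crossover reports from earlier work that "the minimally important clinical difference between groups is 1.5 points for the HIT-6". The sample-size paragraph does not use this value.

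**Not found in the text available.** There is no definition of a positive response, no planned test of proportions, no HIT-6 SD and no assumed mean difference. The sample-size paragraph refers to a Preliminary Studies section that is not part of this text. A response definition or an SD could be given there.

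**The concern.** Power is a property of a particular test on a particular endpoint. Here the power is calculated for a binary outcome, and the trial will be judged on a score. A reader who sees one power figure and one primary endpoint will naturally connect them, and would then read a null HIT-6 result as coming from a trial with 80% power. The plan does not support that reading.

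Two further things are at stake. Because response has no stated definition, a responder analysis added later could use a cut-off chosen after the data are seen. And because sidedness is unstated, a reader who assumes the usual two-sided 5% test would be misled even about the comparison of response rates.

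**Working it through.** **Inputs from the documents:** response rates 0.50 and 0.30; alpha 0.05; power 0.80; 74 per arm; HIT-6 difference of 1.5 points. **Assumed, because the documents give none:** HIT-6 SDs of 4 to 12 points, and the models in step 4 that link response to HIT-6.

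**1. Reproducing the plan's 148.** Normal formula with pooled variance under the null, mean rate 0.40:

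n per arm = [z(alpha)·√(2·0.40·0.60) + z(power)·√(0.50·0.50 + 0.30·0.70)]² / 0.20²

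- One-sided 0.05: (1.645·0.693 + 0.842·0.678)² / 0.04 = 73.1, so 74 per arm and 148 in total. Power at 74 per arm is 80.4% (79.9% at 73).
- Two-sided 0.05: (1.960·0.693 + 0.842·0.678)² / 0.04 = 93.0, so 93 per arm and 186 in total. Power at 74 per arm is 70.4%.

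The one-sided arcsine formula also gives 148. The two-sided variants tried (unpooled, arcsine, continuity-corrected) give 182 to 206. So 148 is a one-sided two-proportion calculation.

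**2. What the planned t test can detect.** With 74 per arm and 80% power (noncentral t, 146 degrees of freedom), the detectable difference is 0.464 SD two-sided or 0.411 SD one-sided.

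**3. The same result in HIT-6 points.** Detectable difference = 0.464 or 0.411 × SD. Power for 1.5 points uses d = 1.5/SD.

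| Assumed SD | Detectable, two-sided | Detectable, one-sided | Power for 1.5, two-sided | Power for 1.5, one-sided |
|---|---|---|---|---|
| 4 | 1.9 | 1.6 | 62% | 73% |
| 6 | 2.8 | 2.5 | 33% | 45% |
| 8 | 3.7 | 3.3 | 21% | 31% |
| 10 | 4.6 | 4.1 | 15% | 23% |
| 12 | 5.6 | 4.9 | 12% | 19% |

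Power for 1.5 points reaches 80% only if the SD is about 1.5/0.464 = 3.2 (two-sided) or 1.5/0.411 = 3.7 (one-sided), or smaller.

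**4. What 50% and 30% imply for the t test.** This depends on how response relates to HIT-6.

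- *Shifted normal.* If response is a cut-off on a normally distributed change with equal SDs, d = z(0.50) − z(0.30) = 0.524. The t test then has 88.7% power two-sided and 93.7% one-sided.
- *Responder/non-responder mixture.* Suppose responders and non-responders differ by a gap g, with SD s within each class in both arms. The mean difference between arms is 0.20·g, and the average variance is s² + g²·(0.25 + 0.21)/2. With k = g/s, d = 0.20k / √(1 + 0.23k²).

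| Gap / within-class SD (assumed) | d | t-test power, two-sided | One-sided |
|---|---|---|---|
| 8 / 8 | 0.180 | 0.19 | 0.29 |
| 8 / 4 | 0.289 | 0.42 (0.415) | 0.54 |
| 12 / 4 | 0.342 | 0.54 | 0.67 |
| 16 / 4 | 0.370 | 0.61 | 0.72 |
| Complete separation | 0.417 | 0.71 | 0.81 |

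Simulations of every row except 8/4 (4,000 runs each) gave t-test power within 0.015 of these values. Two-sided Wilcoxon power was 0.20, 0.53, 0.55 and 0.70 in the same order.

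**The case against.** The strongest reply is that sizing on response rates and then analysing the score is often conservative, because a score carries more information than a dichotomy. The shifted-normal figure of 89% supports this. It stands for that model, but it does not carry over to a treatment that works fully in some patients and not in others, and the documents do not say which description applies.

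Second, the low end of the mixture range rests on inputs chosen for illustration. In the 8/8 case, a cut-off midway between the classes would misclassify about 31% of each class, which is hard to square with a response defined on HIT-6 itself. This is fair. The range shows sensitivity and is not a plausible interval for the trial's power.

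Third, 1.5 points is never adopted as the design target, and a trial may legitimately be sized for a larger expected effect. This also stands. The powers in step 3 describe the only between-group HIT-6 benchmark in the documents; they do not show that a promise was broken.

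Fourth, the Preliminary Studies section may define response or give an SD. That would help to fill the gap, but it could not turn a t or rank-sum test into a test of proportions, nor make 80% the power of that test.

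Last, sidedness is a separate matter that would exist even if the primary test were of proportions. That is true, but it sits in the same sentence and is cured by the same rewording.

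**Conclusion.** The concern holds. The 80% describes a comparison of 50% with 30% at one-sided 0.05; the planned primary test is of HIT-6 at 1 month, and its power is not stated. What follows without any assumed SD is that 74 per arm gives the t test 80% power for 0.46 SD two-sided or 0.41 SD one-sided, and that two-sided power for the response rates is 70%. Everything expressed in HIT-6 points, and every t-test power derived from the 50% and 30% rates, rests on the SDs and models assumed above. Those assumptions lead to power both well above and well below 80%, so the mismatch alone does not show that the trial is underpowered. It should be corrected because the plan's only power figure is attached to the wrong test.

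**What to change.** Restate the sample-size paragraph for the planned test, for example: *With 74 patients per arm and alpha 0.05 [one- or two-sided], the t test on HIT-6 at 1 month has 80% power for a difference of [0.41 or 0.46] SD, which is X points at an SD of S; power for 1.5 points is Y%.* S should be the SD of the quantity actually tested (1-month score or change). It can come from the sponsor's prospective data if these include HIT-6; otherwise give a stated range. If patients with a baseline score of 56 or less are to be left out of the test, replace 74 with the number expected to remain. At 60 per arm, for instance, the detectable difference is 0.52 SD two-sided.

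If the response-rate calculation is kept as background, say that 148 corresponds to one-sided 0.05 and that two-sided power is 70%.

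Add one pre-specified supportive comparison of responders (risk difference with 95% confidence interval) under a single stated definition, preferably the one behind the 50% estimate. Interpret the HIT-6 confidence interval against 1.5 points. These two additions are useful, but the restated power alone cures the mismatch.

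The cost is wording plus one supportive analysis. It needs no more patients, and no new data provided the response definition uses outcomes already being collected. The primary test is unchanged. The drawbacks are one more result to report and possibly a less favourable power statement.

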#### Interim Data Analysis

An interim analysis will be performed of the first 74 patients by the biostatistician. All study participants and other personnel will remain blinded. Safety and efficacy will be evaluated using an O'Brien–Fleming stopping rule of  $p < 0.001$  in order to evaluate for early evidence of treatment efficacy [43].

#### Crossover, Withdrawal, or Missing Data

We will employ an intention-to-treat (ITT) analysis for this trial [44]. Patients that crossover between study arms, withdraw from the study, or for whom there is missing data will all be handled in the same manner: we will conservatively assume that no further benefit will be gained from the initial treatment. As such, the most recent available outcomes data will be extrapolated to all later time points for which no data are available.

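### Carrying the last score forward is called conservative, but its bias between arms can go either way, and the use of scores observed after crossover is left open

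*Combined protocol and SAP*

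**What the plan says.** The section Crossover, Withdrawal, or Missing Data opens with "We will employ an intention-to-treat (ITT) analysis for this trial". It then puts three different events (crossover, withdrawal, missing data) under one rule: such patients "or for whom there is missing data will all be handled in the same manner". The reason given is that "we will conservatively assume that no further benefit will be gained from the initial treatment", and the operation is that "the most recent available outcomes data will be extrapolated to all later time points for which no data are available". No distinction is made between arms.

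Patient Outcome Analysis compares the arms on "The change in HIT-6 from a pre-procedural score", with HIT-6 at one month as the primary endpoint and a t test or Wilcoxon test. It adds that "The same analysis will be employed for all secondary endpoints at each time point". Baseline HIT-6 is collected. On crossover: "Patients will be permitted to crossover to the other treatment arm two months after the procedure". The visible text gives no expected missing rate and names no sensitivity analysis for missing data.

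**The concern.** Assuming no further benefit is cautious when a single treated group is described. In a two-arm comparison the same assumption also removes improvement from the control arm, and Sample Size Determination itself allows for a placebo response of up to 30%. Whether the comparison is pushed towards or away from patching then depends on how many patients are missing in each arm and how those patients really fared. The label promises a direction that the rule does not have, and the carried scores enter the test as if they had been observed.

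The second issue is one of wording. Treating all three events alike, and assuming no further benefit, points to replacing scores observed after crossover by the last score before it. Limiting the extrapolation to time points without data, together with the ITT statement, points to keeping them. Two statisticians could follow the section faithfully and report different late results.

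**Working it through.** The plan attaches no figure to this rule, so there is none to reproduce. From the documents come 74 per arm (Sample Size Determination) and a between-group benchmark of 1.5 HIT-6 points (Patient Outcome Measures and Crossover). Everything else is assumed, because the documents do not give it: SD 8, correlation 0.6 between visits, improvements, missing shares, and a two-sided 5% t test on change from baseline. Baseline is taken to be the carried score unless stated otherwise.

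**1. Formula.** A missing patient with baseline carried contributes a change of 0 instead of the true improvement. So:

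bias in favour of patching = (control missing share × mean true improvement of the missing controls) − (patch missing share × mean true improvement of the missing patched patients).

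**2. No true difference, dropout at random within arm** (20,000 simulated trials per row):

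| Improvement, both arms | Missing control/patch | Formula | Simulated | Rejection |
|---|---|---|---|---|
| 4 | 20%/10% | 0.8 − 0.4 = +0.4 | +0.39 | 6.8% |
| 6 | 15%/5% | 0.9 − 0.3 = +0.6 | +0.60 | 8.2% |
| 6 | 10%/10% | 0.6 − 0.6 = 0 | −0.01 | 4.7% |
| 6 | 25%/5% | 1.5 − 0.3 = +1.2 | +1.19 | 18.1% |
| 6 | 5%/25% | 0.3 − 1.5 = −1.2 | −1.20 | 18.7% |

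A repeat of the 25%/5% row gave 19.3%.

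**3. Missing controls are mainly those who did not improve.** Take the 25%/5% row, but let control missingness rise as improvement falls (log-odds slope per SD of change). The patch term stays at 0.05 × 6 = 0.3.

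- Slope 0.5: bias +0.55, so the missing controls improved by (0.55 + 0.3)/0.25 = 3.4 on average; rejection 8%.
- Slope 1: +0.06, mean improvement 0.36/0.25 = 1.4; rejection 5%.
- Slope 2: −0.50, mean improvement −0.20/0.25 = −0.8; rejection 7%.

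**4. Unequal true gains.** With improvements of 8 (patch) and 4 (control) and 15%/10% control/patch missing, bias = 0.15 × 4 − 0.10 × 8 = −0.2. A true 4.0 shows as 3.8, although patching has fewer missing scores. Break-even is 20%/10%: 0.8 − 0.8 = 0.

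**5. Equal random missingness, true 4-point effect.** With 20% missing in both arms, 4 × (1 − 0.20) = 3.2. With no missing data, the SD of change is 8 × √(2 × 0.4) = 7.16 and the SE is 7.16 × √(2/74) = 1.18; 4/1.18 = 3.40 and 3.40 − 1.96 = 1.44, a power of about 92%. Under carry-forward the simulated power is 76-85%, as control improvement goes from 6 down to 0 points.

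**6. An earlier post-procedure score is carried instead.** Only the change after that score counts. For improvement 6 and 25%/5%: half the gain already in the carried score gives 0.6 points and 7-8% rejection; the full gain gives 0 and 5%. Whether such an earlier HIT-6 score exists cannot be seen in the text.

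**7. Scores after crossover.** On the plan's responder scale (50% v 30%), assume that half of control non-responders cross over and half of those respond. Kept scores give a control rate of 30% + 70% × 0.5 × 0.5 = 47.5% and a difference of 2.5 percentage points. Scores from before crossover give 20. The two readings answer different questions and can be far apart.

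**The case against.** The strongest reply is that the alarming figures depend on assumptions. A gap of 25% to 5% within one month is extreme. Patients and outcome assessors are blinded, the exclusion criteria remove patients who are not expected to complete follow-up, and the prospect of crossover at two months gives disappointed patients a reason to stay. The moderate cases stay well under 1.5 points. All of this stands, and the 18-19% rejection should not carry the point.

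A reader might infer that the rule favours whichever arm has fewer missing scores, or that dropout among disappointed sham patients would inflate the benefit of patching. Neither holds in general. The first needs equal true gains and random dropout within arm (steps 3 and 4). The second can come out near zero or reversed, because baseline is then close to the missing patients' true score. If patching works as planned, the sponsor's word will hold more often than the no-difference examples suggest, but not by design.

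It can also be said that a repeated-measures model is no cure. When missingness rises with the unseen month-1 score, the simulated bias is −0.77 to −0.80 for the model (rejection 10.4-11.1%) and 0.53 to 0.86 for carry-forward (7.5-12.3%). That is right, and it is why a tipping-point analysis is needed under either choice of primary analysis.

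**Conclusion.** The point holds in a limited form. The plan claims a direction for its missing-data rule that the rule does not have. At the 1-month primary the bias can favour either arm or be near zero: about 0.4 to 0.6 points and 7-8% rejection under moderate imbalance with random dropout, up to 1.2 points in either direction and about 19% in an extreme case, and only a loss of effect and power when missingness is equal and random with baseline carried. The sign result is arithmetic; every size rests on the assumed inputs.

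Three stronger readings are not supported. The documents do not show that the rule inflates the benefit of patching. Crossover cannot contaminate the primary, because it starts at two months and the primary is at one. Nor can a false late benefit be asserted: the content of the timeline is not visible, so no visit after two months is confirmed, and the crossover wording matters only if such visits exist. That the wording is unsettled is certain; its consequence is conditional.

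**What to change.** Settle the following before any unblinded look, including the interim analysis of the first 74 patients.

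- Delete the word *conservatively*.
- Analyse HIT-6 with a likelihood-based repeated-measures model (baseline HIT-6, arm, visit, arm-by-visit, unstructured covariance), with the month-1 contrast as primary. Keep carry-forward with the planned t or Wilcoxon test as a sensitivity analysis. If the sponsor prefers the planned test as primary, pre-specify the model as a key sensitivity analysis.
- In either case add a tipping-point analysis.
- State that scores observed after crossover are kept and analysed as randomised for ITT, with a labelled sensitivity analysis using scores from before crossover. If HIT-6 is not collected after crossover, treat those scores as missing.

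In simulation (4,000 trials each, improvement 6 in both arms, no true difference) the model gave −0.01 points and 5.1% rejection at 25%/5% control/patch missing, and 0.01 and 5.4% at 5%/25%; carry-forward gave 1.18 (17.8%) and −1.19 (18.2%). With a true 4-point effect and 20% missing in both arms, the model recovered 4.0 with about 92% power, partly through baseline adjustment.

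The cost is a SAP change and modest programming. The model assumes missing at random, its intervals may be wider than those from carried scores treated as observed, and late contrasts that keep scores after crossover will be diluted.
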